4.3. Clinical data submission

- **4.3.1.** Source documents for all required evaluations and assessments should be stored at local sites for all GVHD evaluations (both acute and chronic). All clinical data required for this study will be input at local sites into the web-based database developed specifically for the Pediatric HCT Biorepository Network. All clinical information should be updated on subjects a least monthly through 1-year post-HCT.
- **4.3.2.** Source documents for 10-15% of required assessments and data will be requested for submission to IUSCC for data control evaluations.

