1. BACKGROUND AND RATIONALE

1.1. Acute Graft-versus-Host Disease (GVHD)

Allogeneic hematopoietic cell transplantation (HCT) is a potential curative therapy for cancers of the blood and bone marrow, including leukemias that represent approximately one third of all cancer cases occurring among children and the leading cause of cancer deaths in children¹. Use of HCT has increased as new techniques have allowed for transplantation in patients who previously would not have been considered HCT candidates. Approximately 30,000 allogeneic HCTs will be performed worldwide in 2020; 20% of allogeneic HCT are performed in the pediatrics population. However, the efficacy of this procedure has been impeded by frequent and severe graft versus host disease (GVHD). The development of GVHD is tightly linked to the beneficial graft versus tumor (GVT) effect, the most potent form of immunotherapy. Nowadays, acute GVHD is measured by clinical symptoms in three organ systems: the skin, liver and gastrointestinal (GI) tract²⁻⁴. Acute GVHD typically occurs between two and eight weeks after transplant, but may occur later⁴, and is often clinically indistinguishable from other causes of clinical symptoms such as conditioning regimen toxicity, infection, or medication. Endoscopic biopsy is often used to confirm the diagnosis^{2,5}, but histologic severity on biopsy has not consistently correlated with clinical outcome^{3,5-7}. A noninvasive, reliable blood biomarker specific for GVHD with strong prognosis information would thus significantly aid in the management of patients with this disorder.

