2.3. Accrual objective and period

- Accrual objective: Sample size 430
- Accrual period: The estimated accrual period is 24 months

2.4. Study duration: Patients will be followed for 12 months following initiation of GVHD therapy or 12 months post-HCT for non-GVHD patients.

- This study will not require any extra clinic visits beyond those required for routine clinical patient care.
- For subjects who consent to the future unspecified use of their biospecimens for research purposes, clinical data collected at any time post-transplant as part of routine clinical care may also be accessed.

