Progression is defined as deterioration in at least one organ without any improvement in others.

No response (NR) is defined as absence of any improvement or progression as defined. Patients receiving secondary therapy (including need to re-escalate steroid dose to \geq 2.5 mg/kg/day of prednisone or equivalent 2 mg/kg/day of methylprednisolone will be classified as non-responders.

Proportion of complete response (CR), Partial response (PR), mixed response (MR), progression, and no response (NR) at day 28 post-therapy (among surviving patients). Scoring of CR, PR, MR, progression, and NR are in comparison to the patient's acute GVHD status on day 0 of systemic therapy for GVHD.

Incidence of additional systemic GVHD therapy given at day 28, and day 56 posttherapy (including for GVHD flare).

Flares are defined as any progression of acute GVHD after an initial response (e.g. earlier CR or PR) that requires re-escalation of steroids or initiation of additional systemic therapy for GVHD.

Steroid dose at day 28 and day 56 post-GVHD therapy

Dose of methylprednisolone will be converted to prednisone by multiplying the methylprednisolone dose by 1.25. Prednisone dose for each patient will be converted to mg/kg. The cumulative prednisone dose for each patient at day 28 will be calculated by adding the doses (end of each week's dose) for each of the four weeks of treatment, divided by the number of days of survival during this interval. The prednisone dose for each patient at day 28 and day 56 will be recorded.

Chronic GVHD is defined per the BMT CTN manual of procedures chapter 2. Symptoms of chronic GVHD if present will be reported using the GVHD symptom record. The incidence of chronic GVHD at 6 and 12 months will be computed.

Non-relapse mortality (NRM) at day 180 post-therapy for GVHD patients and NRM at day 180 post-HCT for patients without GVHD will be computed. The events for NRM are death due to any cause other than relapse of underlying malignancy.

Overall survival, GVHD-free survival at day 180 and 360 post-therapy for GVHD patients and at day 180 and 360 post-HCT for patients without GVHD will be computed.

Relapse at day 360 post-HCT will be computed.

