Children with chronic GVHD can present with skin, GI, eye or systemic disease leading to failure to thrive, persistent immunodeficiency, or pulmonary disease. Chronic "eczema' or dry skin are common manifestations of mild chronic GVHD of skin. Liver disease can present as asymptomatic hyperbilirubinemia or elevated alkaline phosphatase. As children can have marked elevations in alkaline phosphatase during growth spurts, children with this laboratory abnormality should have a fractionated alkaline phosphatase to confirm that the band is from the liver and not from bone before a diagnosis of chronic GVHD is made. Children with chronic GVHD of the upper GI tract may have chronic anorexia or poor growth due to malabsorption. Rather than losing weight, children may "fall off" their growth curve with decreased gains in height or weight velocity. In children < 2 years of age, this may also affect growth of head circumference. Chronic GVHD may also cause persistent low or intermediate immunodeficiency. In addition to increasing the risk of opportunistic infection, this may cause GI dysfunction and lead to malabsorption, low IgG (due to protein losing enteropathy), lactose deficiency, and poor growth. Duodenal intubation with quantitation of pancreatic enzymes is useful in these children. If pancreatic enzymes are low, children may benefit from supplementation of pancreatic enzymes.

See Appendix D for a sample of chronic GVHD data record for use in this trial.

Summary of Required Assessments

- For all subjects
 - complete acute GVHD staging and grading information including assessment of rash, diarrhea, nausea/vomiting, liver function and weight at day 7, 14, 21, 28, 56, 100, and 180 post-HCT
 - Chronic GVHD evaluation at day 100, 180 and 360 post-HCT (please refer to Appendix D for GVHD assessment forms)
 - Infections requiring therapy up to 360 days post-HCT
 - Baseline weight
 - Blood samples for laboratory studies and future use at day -7, 7, 14, 21, 28, 56,100,180, and 360 post-HCT
- For subjects who develop GVHD or GVHD-like symptoms,
 - recommended biopsy of involved tissue (this is standard of care, not research)
 - Complete acute GVHD staging and grading information including assessment of rash, diarrhea, nausea/vomiting, liver function and weight at onset of symptoms and 28 and 56 days post-systemic GVHD therapy
 - Steroid dosing information weekly until day 56 after initiation of steroids

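### Site data collection ends on the transplant clock, so scheduled collection does not support day-360 post-therapy survival and GVHD-free survival in GVHD patients

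*Protocol*

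**What the plan says.** The protocol uses two time origins for GVHD patients.

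The therapy clock appears in the study duration and the outcome definitions:
- Section 2.4 (and the synopsis): "Patients will be followed for 12 months following initiation of GVHD therapy or 12 months post-HCT for non-GVHD patients".
- Section 3.3: "Overall survival, GVHD-free survival at day 180 and 360 post-therapy for GVHD patients", and also "Non-relapse mortality (NRM) at day 180 post-therapy for GVHD patients". The latter is part (a) of the primary objective.

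The transplant clock appears in the instructions a site would follow:
- Section 4.3.1, data entry: "All clinical information should be updated on subjects a least monthly through 1-year post-HCT".
- Section 4.2, Summary of Required Assessments, acute grading for all subjects: "liver function and weight at day 7, 14, 21, 28, 56, 100, and 180 post-HCT".
- Same list, chronic disease: "Chronic GVHD evaluation at day 100, 180 and 360 post-HCT".

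The only GVHD grading scheduled on the therapy clock is in the same summary: "liver function and weight at onset of symptoms and 28 and 56 days post-systemic GVHD therapy".

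On the usual timing of onset, section 1.1 says: "Acute GVHD typically occurs between two and eight weeks after transplant, but may occur later".

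The SAP states that all subjects were followed for at least 1 year and gives no time origin. It lists analyses of non-relapse mortality and acute GVHD, but none of overall survival or GVHD-free survival.

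**The concern.** A site that does exactly what section 4.3.1 and Table 3 require will have finished its work on a typical GVHD patient before that patient reaches day 360 post-therapy. Section 2.4 promises the longer follow-up, but no operational section implements it.

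If entry did end at 1 year post-HCT, day-360 survival would be censored before its own time point, or would be read off day 360 post-HCT without anyone saying so. The lost time grows with later onset. Patients without GVHD are measured from transplant and are covered to day 360, so the two groups' day-360 figures would rest on unequal data.

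GVHD-free survival has a second problem. It needs GVHD status, and the protocol does not say which GVHD events count or where they are read from. An acute flare after the last scheduled grading could go unrecorded and be counted as GVHD-free.

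**Working it through.** No figure in the plan needs reproducing; the check is calendar arithmetic.

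Inputs:
- Required data entry ends 1 year post-HCT, taken as day 365 (section 4.3.1).
- Last chronic GVHD evaluation is day 360 post-HCT, and last acute grading is day 180 post-HCT (section 4.2). Day 56 post-therapy is later than day 180 post-HCT only if therapy starts after day 124 (124 + 56 = 180).
- Typical onset is 2 to 8 weeks, that is, days 14 to 56 (section 1.1). Appendix C describes day 14 as a median of 14 days before GVHD, which implies a median onset near day 28 (14 + 14).
- Assumption: systemic therapy starts at onset, on HCT day t.

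Formulas:
- Day 180 post-therapy is HCT day t + 180. It lies (t + 180) − 180 = t days after the last scheduled acute grading.
- Day 360 post-therapy is HCT day t + 360. It lies (t + 360) − 365 = t − 5 days after required entry ends, and (t + 360) − 360 = t days after the last chronic evaluation.
- Required entry reaches therapy day 365 − t.

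| t | Day 180 post-therapy (HCT day) | Days past last acute grading | Day 360 post-therapy (HCT day) | Days past required entry | Last therapy day with required entry |
|---|---|---|---|---|---|
| 14 | 194 | 14 | 374 | 9 | 351 |
| 28 | 208 | 28 | 388 | 23 | 337 |
| 56 | 236 | 56 | 416 | 51 | 309 |
| 100 | 280 | 100 | 460 | 95 | 265 |

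Limits of coverage:
- Day 360 post-therapy lies within required entry only if t + 360 ≤ 365, that is, t ≤ 5.
- Day 180 post-therapy lies within required entry if t + 180 ≤ 365, that is, t ≤ 185. Non-relapse mortality and overall survival at day 180 post-therapy are therefore covered for typical onset and well beyond it.
- For GVHD-free survival at day 360 post-therapy, the last scheduled acute grading is t + 180 days earlier: 194 days for t = 14 and 236 days for t = 56.

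**The case against.** The strongest reply is that section 2.4 governs. It already gives GVHD patients 12 months from therapy start, which covers day 360 post-therapy. Section 4.3.1 sets a minimum frequency of entry; it does not forbid entry after 1 year. This stands. A reader might infer that the day-360 outcomes fall outside the data, or that the two sections cannot both be met. The documents support neither: a site that updated monthly to 1 year and then kept following the patient would satisfy both. What remains is that nothing in section 4 requires the later entry.

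Second, a treated flare has other routes into the data. Monthly updates cover all clinical information to 1 year post-HCT, which includes day 180 post-therapy for typical onset. Table 3 records other GVHD medications to day 360, and section 3.3 collects the maximum acute grade and its day. This also stands, so it is not shown that GVHD-free survival would look better than it is. It is not a complete answer, because Table 3 ends both acute grading and steroid dose at day 180 post-HCT, and flares are defined partly by steroid re-escalation.

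Third, the outcomes are section 3.3 correlatives, and Cox regression handles administrative censoring. The first part stands and limits the importance. The second helps with hazard ratios, not with a survival proportion at day 360. If entry did stop at day 365 and no patient started therapy before day 14, nobody would be at risk after therapy day 351.

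Two further points do not close the gap. Later routine data may be accessed only for subjects who consented to future use, and the SAP's minimum of 1 year has no stated origin.

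**Conclusion.** The point holds as an unimplemented follow-up period. Sections 2.4 and 3.3 promise outcomes on the therapy clock, while section 4.3.1 and Table 3 require collection on the transplant clock. For therapy starting on days 14 to 56, scheduled collection falls 9 to 51 days short of day 360 post-therapy, so overall survival and GVHD-free survival there are not supported by it. GVHD-free survival at day 180 post-therapy has no scheduled acute grading in its last 14 to 56 days.

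A reader might infer that the primary non-relapse mortality outcome is affected. It is not, for therapy starting up to about day 185.

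The figures assume that 1 year means day 365 and that therapy starts at onset. Later therapy widens the gap. The documents do not show when data entry actually stopped. The change is worth making because it decides which data exist at stated time points, but no primary or secondary endpoint in sections 3.1 and 3.2 depends on the day-360 outcomes.

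**What to change.** Reconcile section 4.3.1 and Table 3 with section 2.4. For treated GVHD patients, required entry should run to the later of 1 year post-HCT and 360 days after the start of systemic GVHD therapy. Vital status, relapse, and acute and chronic GVHD status should be abstracted from the chart at days 180 and 360 post-therapy. State which GVHD events end GVHD-free survival and which records supply them.

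The cost is protocol wording and about 9 to 51 more days of chart abstraction per typical GVHD patient (95 days if therapy starts on day 100), with no added visits or samples. Status taken from charts will be less uniform than scheduled grading.

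The SAP reports that accrual ended in 2018, so editing the schedule may no longer change what was collected. Where data were closed at 1 year post-HCT, either censor at the last required update or report these outcomes at a time point the data cover. Limit GVHD-free survival to the period in which GVHD status was recorded. State the time origin, and if it moves from therapy to transplant, say so openly, because that changes the outcome and not only its label. The SAP should also give the origin of its 1-year minimum follow-up.

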4.4. Sample Processing

After collection, samples will be processed, aliquoted, and frozen utilizing the standard operating procedures developed by the [name] laboratory and the Indiana CTSI Specimen Storage Facility (described below in the section entitled "Storage"). SOPs for sample processing established by the [name] laboratory will be followed for all

processing procedures. A manual for sample processing for this study will be provided to all participating sites. These can also be provided when requested and during audits.

4.5. Sample Storage and Tracking

A global unique identifier is randomly assigned to each sample and derivative. Samples of the same person can only be linked by authorized persons who have access to the All sample data will be organized and stored in the data in the database. SpecimenTrack system from Remedv Informatics (http://www.remedyinformatics.com/product/specimentrack/). A series of biobanking electronic forms will be created to track the collection, inventory, and distribution of HSCT biosamples. Since SpecimenTrack can be readily integrated with the HSCT Registry, the samples will always be associated with their clinical, lab, and genotypic annotations. Both the HSCT Registry and SpecimenTrack will be deployed in a HIPAA aligned environment and supported by staff trained in HIPAA best practices. Both systems are enterprise level systems with powerful and granular control of user permissions, roles, and administration. The HSCT systems will be supported by members of the Indiana CTSI informatics team, who are experienced with deploying, maintaining. and providing user support for systems such as REDCap (https://en.wikipedia.org/wiki/Redcap %28Research Electronic Data Capture%29). Both Remedy systems, MosaicBuilder and SpecimenTrack, are web applications accessible through a web browser using HTTPS, thus allowing both local and distant collaborators to use the system in an encrypted and manner.

The Pediatric HCT Bio-repository Network samples will be stored in the Indiana Biobank in affiliation with the Indiana CTSI Specimen Storage Facility (SSF). The Indiana CTSI manages a Specimen Storage Facility dedicated to sample storage in accord with International Society of Biologic and Environmental Repositories (ISBER) Best Practices and protocol defined sample parameters. The SSF is located in the new Wells Children's Clinical Research Center in Riley Children's Hospital.

The SSF is directed by [name], CSO, Indiana CTSI, and operates under the Indiana CTSI Specimen Storage Facility Advisory Committee, [name], Chair. Quality Compliance oversight is provided by [name], Cincinnati Children's Hospital Medical Center (CCHMC) Office of Research Compliance and Regulatory Affairs (ORCRA). The approaches and day-to-day activities of the SSF are managed by QA reviewed SOPs organized into the following chapters:

Administration and Quality Oversight: SOP SF-1-1 through SOP SF-1-13. This collection of procedures defines maintenance of SOPs, Scope of Services, Organization of the SSF, Management of the SSF, Training, Controlled Document Management, Safety Quality Management, Deviation Management, Out-of-Specification Management, Audit Management, Commissioning/ Validation/ Revalidation policies and Housing for Good Laboratory Practices. The central

approach of the SSF is to provide the sample storage controls for PI owned collections rather than to manage the protocols under which the specimens are collected and released. These SOPs control all procedures associated with specimen intake and management while the specimens are located in the SSF.

- Facility Management: SOP SF-2-1 through SOP SF-2-4. The four facility systems within the SSF that are critical to ensuring storage compliance with ISBER and specimen quality are Mechanical Freezer Storage Room Controls, Liquid Nitrogen System and Freezer Room Controls, Controlled Access and Alarm Management and Response. These SOPs define procedures for monitoring and responding to situations within the facility critical to ensuring sample integrity.
- Equipment Management: SOP SF-3-1-SOP SF-3-9. All equipment in the SSF is maintained, monitored, and function verified according to strict specifications included in the SOPs for Refrigerators and Freezers, Liquid Nitrogen Freezers, Pipettes, Centrifuges, Biological Safety Cabinets, Timers, Thermometers, Personal O2 monitors, and Emergency Escape Breathing Apparatus to be used in the event of a large-scale liquid nitrogen release event. These SOPs are written to ensure that equipment is used, calibrated, and generally maintained to support quality specimen management.
- Specimen Processing: SOP SF Chapter 4. This group of SOPs defines the technical steps for supporting storage of the multiple collections according to the defined parameters of each. This chapter of SOPs is ever evolving with the overarching SOPS within the chapter being SOP SF-4-1 Managing Requests for Sample Support and SF-4-4 Managing Sample Receipt, Log-in and Tracking.
- These SOPs are available on-line at IndianaCTSI.org/ictsissf/sops or can be provided for review by contacting the SSF Director ([name]) or Chair of the SSF Advisory Committee ([name]). The Indiana CTSI SSF is a CTSI Designated Core Laboratory signifying that operating policies and charges are reviewed at least annually by the CTSI Translational Technology Resources (TTR) core oversight committee. All personnel in the SSF who have access to PHI have completed human subjects training.

4.7. HSCT Multi-Center Informatics Infrastructure

Data obtained during this clinical trial will be collected at six cancer centers: SKCCC, DFCI, FHCRC, IUSCC, TXCCC and CNMC. Since this proposal involves a very large amount of data to be collected from a multi-center clinical trial as well as a large amount of proteomic data, we have put procedures in place to ensure the integrity of the data transmitted and to allow consistent handling of the clinical data at all sites. The clinical and laboratory data collected will be organized and stored in the HSCT Registry, constructed using the MosaicBuilder platform from Remedy Informatics (http://www.remedyinformatics.com/mosaic-platform/mosaic-builder-edition-for-it-

professionals/). Data will either be imported directly from the Cerner Electronic Medical Record system, exchanged using flat files, or entered manually into the system using electronic forms. The Mosaic enterprise level platform is deployed and maintained as a service by the Indiana Clinical Translational Sciences Institute, and enables the creation of biobanks that are integrated with clinical, lab, genotypic, and phenotypic data. This platform is engineered to support complex workflows, and is deployed in a HIPAA aligned environment such that the server, database, and application, are located at secured locations and supported by professional staff trained in HIPAA best practices. The Mosaic platform is also ontologically aware so that the semantic definition of the data can be standardized. This further enables meaningful data integration and querying. All of these factors ensure that the HSCT Registry will be a secure, stable, robust and extensible research informatics platform for the future.

4.8. Future Use Sample analysis

One objective of this protocol is sample and clinical data collection for future unspecified research. It is anticipated that some of the sample analyses may be carried out prior to specific research questions or projects using the advanced diagnostic techniques listed below; however, the data generated using these analyses will only be released for data analysis once there is IRB approval for the investigation of a specific hypothesis-driven research question.

The sample analyses that may be carried out as part of this protocol may include, but are not limited to:

- Genomics
- Proteomics
- Cytokine analyses
- Flow cytometry

Metabolomics

These analyses will generally be performed at one of the six participating sites in the PHCTBN. On occasion, the analyses of research samples will involve collaborators at other institutions in order to have access to the most technologically advanced or cost effective techniques. All samples analyzed at another institution as part of this project will maintain the bar code assigned to the subject on enrollment in this study. This process allows for use of a unique identifier that the principal investigator of this study may use to link the data to other subject information but eliminates the possibility of transmission of privileged health information. Samples analyzed at another center will generally be entirely consumed by the research procedures. Any residual will be destroyed at the end of this project or returned to the Indiana University storage facility.

